9.4 Stair Ascent/Descent

This test is a physical performance measure that assesses the time it takes the subject to ascend and/or descend a flight of twelve, 18-cm high steps with a depth of 28 cm. Participants will be asked to complete the test as quickly as they feel safe and comfortable. Handrails are allowed if required, but subjects are encouraged to use just their legs for stair negotiation. Time to negotiate the stairs is measured to the nearest one hundredth of a second with by stationary timing devices a stopwatch. A partial practice trial is completed to gauge subject capability and ensure safety monitoring, then the mean of two subsequent trials is used for analysis. Assistive devices are

Use of Blood Flow Restriction + Standard of Care Physical Therapy to Improve Functional Outcomes after
Anterior Cruciate Ligament Reconstruction
PI: [name].
Institution: UAMS
Sponsor: UAMS

allowed only if the participant is unsafe or could not complete the test without a cane or walker. The use of assistive devices, as well as use of the handrail, is recorded.

9.5 Dual Energy-Xray Absorptiometry

This test will be used to measure body composition (fat mass, lean mass, and percent body fat). Subjects will be asked to remove all metal, thick clothing, and heavy plastic which could interfere with the DEXA scans. The subject's ID, age, ethnicity, height and weight will be entered into the computer prior to the scanning. The subject will be asked to lie down on the DEXA table in the supine position. The participant will be centered on the table within the scanning area. The subject's shoulders and hips will be centered, and the hands will be placed by the side of the legs in a prone position. Subjects will be instructed to remain still for the duration of the full-body scan. A trained DEXA technician will perform and analyze all scans. Subjects will be asked to fast for 8 hours, avoid caffeine and alcohol for 12 hours, and avoid strenuous exercise for 24 hours prior to this procedure.

9.6 InBody Bioelectrical Impedance Analysis

This test will measure total body and segmental water, to be combined with the DEXA measures for a more accurate body composition estimates. To obtain measurements, subjects are asked to stand barefoot on a calibrated scale to obtain subject weight. Once subject height, sex, and age are entered into the device, subjects are instructed to hold onto two handles and remain still while an imperceptible electrical current runs between electrodes in the handles and scale. Total assessment time is <2 minutes. Subjects will be asked to fast for 8 hours, avoid caffeine and alcohol for 12 hours, and avoid strenuous exercise for 24 hours prior to this procedure.

9.7 Clinical Data Collection

Use of Blood Flow Restriction + Standard of Care Physical Therapy to Improve Functional Outcomes after Anterior Cruciate Ligament Reconstruction
PI: [name].
Institution: UAMS
Sponsor: UAMS

9.7.1 Quantitative Pain Scores: study staff will obtain pain scores that were assessed by physical therapists by reading the visit notes written by the therapist in Epic. Scores will be captured up through visit 5.

9.7.2 Fear and Avoidance Beliefs Questionnaire: study staff will obtain these scores that were documented by physical therapists by reading the visit notes written by the therapist in Epic. Scores will be captured up through visit 5.

9.7.3 Range of Motion: study staff will obtain ROM values that were assessed by physical therapists by reading the visit notes written by the therapist in Epic. Values will be captured up through visit 5.

9.7.4 Rehabilitation Volume: study staff will obtain total exercise volume, duration, and load from physical therapist's notes in Epic.

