2.1 Significance

Participants will attend their usual physical therapy visits and be randomized to receive PBFR or standardized rehabilitation. This use of a current and standardized clinical program and experienced physical therapists determines both suitability and clinical

Use of Blood Flow Restriction + Standard of Care Physical Therapy to Improve Functional Outcomes after
Anterior Cruciate Ligament Reconstruction
PI: [name].
Institution: UAMS
Sponsor: UAMS

translation. We propose to evaluate physical functional outcomes with a blinded tester and quantifiable measures that are standards in our hands. The goal of this pilot project is to demonstrate the potential to steepen the healing curve after ACL repair. The improved healing time will translate to an earlier return to weight bearing and the resumption of normal activities or duty. In addition to pre-test and post-test, we will incorporate two additional testing points over the length of the physical therapy sessions. This testing schedule will identify progress in functional outcome recovery over the course of rehabilitation. If successful, this rehabilitative modality may allow rehabilitation economics to be truncated and an earlier return to function. This pilot study will provide data, process refinement, and methods confirmation in preparation for a larger project submission.

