5.0 Study Visits

Use of Blood Flow Restriction + Standard of Care Physical Therapy to Improve Functional Outcomes after
Anterior Cruciate Ligament Reconstruction
PI: [name].
Institution: UAMS
Sponsor: UAMS

Subjects will be required to wear a mask. If they do not have one, a mask will be provided to them by the study staff.

Visit 1: This visit will take place at the UAMS RIOA prior to surgery. At this visit, informed consent discussion will be held. Study staff will use appropriate PPE. This visit is expected to take less than about one hour. If a subject consents, their vital signs will be measured (blood pressure, oxygen saturation) while at rest for at least 10 minutes for exclusion criteria. Randomization will occur. [name] will be notified via email as to which group each enrolled subject has been randomized. He will then communicate this to the relevant physical therapists at the Col. Glenn facility.

Visit 2: This fasted visit will occur approximately 7-10 days before surgery. Subjects will be asked to fast for 8 hours, avoid caffeine and alcohol for 12 hours, and avoid strenuous exercise for 24 hours prior to this visit. Subjects will undergo body composition testing (DEXA, InBody). After a 5 minute warm up (stretching/walking/cycling as tolerated), strength testing of each leg, and 10-meter walking speed test will commence. This visit is expected to take about 1 hour.

Visit 3: This visit will take place at the UAMS RIOA approximately 8 weeks after surgery. Subjects will be asked to fast for 8 hours, avoid caffeine and alcohol for 12 hours, and avoid strenuous exercise for 24 hours prior to this visit. At this visit, a 5-minute warm up, physical, functional, and body composition testing (DEXA, InBody) will take place (see Study Calendar). Future study visits will be scheduled. This visit is expected to take about 1 hour.

Visit 4: This visit will take place at the UAMS RIOA approximately 12 weeks after surgery. Subjects will be asked to fast for 8 hours, avoid caffeine and alcohol for 12 hours, and avoid strenuous exercise for 24 hours prior to this visit. At this visit, a 5-minute warm up, physical, functional, and body composition testing (DEXA, InBody) will

Use of Blood Flow Restriction + Standard of Care Physical Therapy to Improve Functional Outcomes after
Anterior Cruciate Ligament Reconstruction
PI: [name].
Institution: UAMS
Sponsor: UAMS

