take place (see Study Calendar). Future study visits will be scheduled. This visit is expected to take about 1 hour.

Visit 5: This visit will take place at the UAMS RIOA approximately 16 weeks after surgery. Subjects will be asked to fast for 8 hours, avoid caffeine and alcohol for 12 hours, and avoid strenuous exercise for 24 hours prior to this visit. At this visit, a 5-minute warm up, physical, functional, and body composition testing (DEXA, InBody) will take place (see Study Calendar). Future study visits will be scheduled. This visit is expected to take about 1 hour.

As part of PT, subject's level of pain will be ascertained using a 0-10 point scale at the onset of their PT visits. They will also be asked to complete the Fear-Avoidance Beliefs Questionnaire at some visits. The ROM of their surgical knee will be measured at certain times. In addition, progression towards UAMS' 'Return to Sport' measurements are performed and documented. Some of these data elements will be retrieved from the therapist's notes in Epic by study staff.

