6.0 Blinding

The study is a single-blind, randomized, controlled trial (RCT). While participants cannot be blinded since BFR is the intervention being evaluated, key investigators and outcomes assessors will be blinded to treatment assignment, making this a single-blind RCT from the investigators' perspective.

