8.0 Intervention Description

All subjects will have the standard physical therapy visits conducted by the PTs at the Colonel Glenn facility. Participants will undergo standard physical therapy sessions at UAMS' Colonel Glenn facility either with or without the use of the BFR apparatus. Subjects will progress through the goals set by their therapist as their condition permits. Physical Therapists will be the same (Colonel Glenn therapists) for both intervention and standard of care groups to standardize treatment. The physical therapists participating in the study have all demonstrated proficiency in the BFR approach. Briefly, the BFR apparatus consists of an electronically controlled pneumatic tourniquet(s) that is placed (in this study) on the upper thigh(s) and inflated during exercise. The control mechanism continuously adjusts the air pressure to maintain the operator-chosen percentage of arterial occlusion (e.g. 75%) as determined by the blood pressure of that limb for a determined amount of time (e.g. for the duration of 4 sets of 30:15:15:15 ~~3 sets of 8~~ repetitions of knee flexion/extension). The tourniquet is deflated at specific intervals. The BFR apparatus is used primarily in the early stages of rehabilitation with the goal of increasing the strength and endurance of that limb at a faster rate than performing the exercises without BFR.

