10.3 Data Handling and Recordkeeping

Physical Therapy sessions will be documented by Physical Therapists in EPIC. Data will be transferred from EPIC to the UAMS data warehouse and then imported into REDCap so no mistakes are introduced between data collection and data analysis. Outcome testing data (without identifiers) will be entered into REDCap to facilitate analyses. These files are maintained on secure password-protected UAMS servers. Approximately 7 years after study completion, electronic records will be destroyed per UAMS disposal guidelines. At no time shall Protected Health Information be released to non-study personnel.

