10.4 Data Access

All subjects will be assigned a unique identifying code or number. The key to the code (the instrument associating the data with subject identity) will be kept on a password-protected UAMS server. Only study staff members will have access to the code and information that identifies the subject in this study. This file will be deleted approximately seven years after data analysis is completed.

Use of Blood Flow Restriction + Standard of Care Physical Therapy to Improve Functional Outcomes after
Anterior Cruciate Ligament Reconstruction
PI: [name].
Institution: UAMS
Sponsor: UAMS

Epic medical record will be accessed by study staff to extract specific data from the PT notes for exercises performed, noting repetitions, sets, resistance, occlusion, pain level, Fear-Avoidance Beliefs questionnaire, and ROM measurements.

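### Section 6.0 claims blinded outcome assessors without exception, but ROM, pain and fear-avoidance are not blinded, and blinding of the RIOA tests and of MVC is not protected

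*Combined protocol and SAP*

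**What the plan says.** Section 6.0 states that "key investigators and outcomes assessors will be blinded to treatment assignment", and names only participants as unblinded. Section 2.1 presents this as a strength of the study: "We propose to evaluate physical functional outcomes with a blinded tester".

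Section 9.0 (Outcome Measures) includes 9.7, which takes pain, fear-avoidance and ROM from physical therapy records. For ROM the wording is "study staff will obtain ROM values that were assessed by physical therapists by reading the visit notes written by the therapist in Epic"; pain and fear-avoidance follow the same route. On the therapists, Section 5.0 says of the person notified of each allocation: "He will then communicate this to the relevant physical therapists at the Col. Glenn facility". Section 8.0 adds: "Physical Therapists will be the same (Colonel Glenn therapists) for both intervention and standard of care groups".

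Section 10.4 has study staff go into the Epic therapy notes for the exercises performed, "noting repetitions, sets, resistance, occlusion, pain level", the fear-avoidance questionnaire and ROM. Section 10.3 describes another route for therapy data: "Data will be transferred from EPIC to the UAMS data warehouse and then imported into REDCap".

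Section 9.2 allows an MVC result obtained in physical therapy within about a week to stand in for the study's own test.

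**The concern.** The blinding claim is broader than the procedures support, in three places. The ROM assessor knows the arm. The notes that study staff read disclose the arm, and study staff is also the term used for the people who run the RIOA tests. And one strength outcome can be supplied from outside the study's testing session.

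MVC, the fast walk, the stair tests and the Y-balance test all depend on how hard the subject tries. A tester who knows the arm can encourage subjects unequally without meaning to. The protocol criticises an earlier BFR study for lack of blinding, and Section 10.1 says the pilot's purpose is to supply data for powering later work. Any assessor bias would therefore carry into the next study's assumptions under a single-blind label.

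**Working it through.** No formula applies. The documents contain no power calculation, assessor-bias figure or blinding-integrity measure to reproduce. The check sets the sections side by side.

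**Step 1: who produces each value, and whether that person knows the arm.**

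| Outcome | Who produces the value | Knows the arm? | Tested at 0.05 under 10.1? |
|---|---|---|---|
| ROM (9.7.3) | Treating therapist | Yes (5.0, 8.0) | Unclear; 10.1 does not list its functional outcomes |
| Pain (9.7.1) | Participant rates, therapist records | Yes, both | Not named; neither strength nor function |
| Fear-avoidance (9.7.2) | Participant completes, therapist documents | Yes, both | Not named; neither strength nor function |
| MVC tested at RIOA (9.2) | RIOA tester | Blinded by 6.0, not protected | Yes, strength |
| MVC taken from therapy (9.2) | Tester not specified | No blinding condition | Yes, strength |
| Walk, stairs, Y-balance (9.1, 9.3, 9.4) | RIOA tester | Blinded by 6.0, not protected | Yes, function |

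ROM contradicts Section 6.0 directly. For pain and fear-avoidance the source of the score is the participant, whom Section 6.0 already calls unblinded. Blinding the therapist would not cure that, but a reader of 6.0 is not told that these outcomes fall outside the claim.

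**Step 2: who reads the notes.** Sections 9.7 and 10.4 assign extraction to study staff, and 10.4 includes occlusion, which is recorded only where the cuff is used. Sections 9.1 and 9.3 have study staff accompany the walk test and conduct the Y-balance test, and 9.2 has them handle MVC results. No section says that extractors and testers are different people, that occlusion is masked, or that extraction waits until testing ends.

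**Step 3: the two data routes.** Section 10.3 moves therapy data by electronic transfer, while 9.7 and 10.4 describe reading notes. The transfer could reduce exposure, but 10.3 does not say which fields it carries, and occlusion imported into REDCap would still be visible to a tester with access.

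**Step 4: MVC substitution.** The Study Schema starts the prescribed therapy after surgery, so substitution can arise at Visits 3, 4 and 5. Section 10.1 tests the mid-point and final visits, which the schema identifies as Visits 4 and 5, so substituted values can enter both tested comparisons. The completion target is 20 at 1:1, or 20 / 2 = 10 per arm. One substituted value is therefore 1 / 10 = 10% of an arm's MVC data at that visit. How often substitution would occur is not stated.

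**The case against.** The best defence is that 9.7 was never meant as blinded endpoint data. Its title is Clinical Data Collection, and it also holds rehabilitation volume, a measure of exposure. The test order in 9.8 and the Study Calendar both omit its items. The Specific Aim is muscle mass, strength and function. Section 2.1 promises a blinded tester only for physical function, and 10.1 tests only strength and function. This is persuasive for pain and fear-avoidance and arguable for ROM. It does not rescue Section 6.0, which carries no such limit, and it does not touch the note-reading or MVC gaps.

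A second defence is that the RIOA measures are instrumented: stationary timers for the walk and peak torque from a dynamometer for MVC. That limits error in reading the result, but not differences in effort.

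Three stronger readings are tempting and not supported:

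- A reader might infer that the RIOA testers are in fact unblinded. Study staff is a generic term, and 6.0 commits assessors to being blinded. The documents fail to separate the roles; they do not show that they overlap.
- A reader might infer that all three therapy-record outcomes are irregularly timed. Section 5.0 places pain at the start of therapy visits. Only the questionnaire and ROM are loosely scheduled ("The ROM of their surgical knee will be measured at certain times").
- A reader might attach an inflated false-positive rate to the 9.7 outcomes. That would need an assumed bias size, a 0.05 test that 10.1 does not clearly assign to them, and, for ANCOVA, a pre-surgery value that Visit 2 does not collect.

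**Conclusion.** The point holds as a mismatch between a central design claim and the written procedures. For ROM the claim in 6.0 is wrong as stated. For pain and fear-avoidance it is misleading, because unblinded participants supply the scores. For the RIOA tests (MVC, walk, stairs, Y-balance) blinding is claimed but not protected, and a breach is possible rather than shown. For MVC there is an additional route by which values with no blinding condition can enter an analysis tested at 0.05.

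The extent is three outcomes outside the claim, four types of effort-dependent test without a safeguard, and one tested outcome open to substitution. The bias itself cannot be sized from the documents. The conclusion rests on the text alone and on no assumed effect, variance or correlation. It merits correction, mainly because it can be made without new assessments.

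**What to change.** 1. **Sections 9.7 and 10.4.** State that anyone who runs RIOA tests does not open a subject's therapy notes or occlusion fields, in Epic or REDCap, until that subject's Visit 5 is complete. Extraction can be done after that point, by existing staff who do no testing, or by the 10.3 transfer where it carries the needed fields. Reconcile 10.3 with 9.7 and 10.4 so that one route is described for each data item. The restriction falls on testers only and leaves the adverse event review in 11.6 as it is.
2. **Sections 6.0 and 10.1.** Limit the blinding claim to outcomes tested at RIOA by the blinded tester. State that pain, fear-avoidance and ROM are unblinded and will be reported descriptively.
3. **Sections 9.2 and 10.1.** Record the source of every MVC value, flag those from therapy as unblinded, and repeat the MVC analysis without them.

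The cost is a narrower blinding claim, later extraction of some therapy data, no formal test of pain, fear-avoidance or ROM, and one extra sensitivity analysis. With about 10 subjects per arm, that analysis will lose precision if many MVC values come from therapy.

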9.8 Order of Outcome Tests

Outcome measures will be performed in the following order for every visit:

DXA scan

InBody composition

MVC

10-meter walking speed

Stair ascent/descent

Y-balance

Formatted: Font: (Default) Arial, Bold, Font color: Auto

Formatted: Heading 2, Adjust space between Latin and Asian text, Adjust space between Asian text and numbers

Formatted: Font: (Default) Arial, Bold

10.0 Data Analysis, Use and Handling

10.1 Statistical Analysis/Power Calculations

Descriptive statistics for numeric outcome measures as well as demographic and clinical characteristics will be reported as means and standard deviations or medians and interquartile ranges, as appropriate. For each strength and functional outcomes, the difference between the two groups by the mid-point and final visit will be tested with two-sided hypotheses at a significance level of 0.05. For each parameter, an analysis of

Use of Blood Flow Restriction + Standard of Care Physical Therapy to Improve Functional Outcomes after
Anterior Cruciate Ligament Reconstruction
PI: [name].
Institution: UAMS
Sponsor: UAMS

covariance (ANCOVA) model will include terms for the main model effect of intervention group with pretest as a covariate for each parameter. For each group comparison, homogeneity of variances, normality, and parallel posttest-pretest slopes will be assessed. In the case of non-normal distributions, data transformations will be evaluated and applied if appropriate. Otherwise, for any group comparison with unmet ANCOVA assumptions, an alternative analysis such as generalized linear mixed models will be pursued instead. Statistical analysis will be performed using SAS version 9.4. The objective of this pilot work is to obtain adequate data on which to power future studies and project submissions.

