11.0 Risks and Benefits	17
11.1	17
Physical, Functional, Range of Motion Testing	17
11.2 Blood Flow Restriction device	17
11.3 DEXA Scan	18 17
11.4 InBody Bioelectrical Impedance scan	18
11.5 Confidentiality	18
11.6 Data Safety Monitoring Plan	18
12.0 Ethical Considerations.....	18
13.0 References	19

Use of Blood Flow Restriction + Standard of Care Physical Therapy to Improve Functional Outcomes after
Anterior Cruciate Ligament Reconstruction
PI: [name].
Institution: UAMS
Sponsor: UAMS

List of Abbreviations

ACL	Anterior cruciate ligament
BFR	Blood Flow Restriction
CRF	Case Report Form
DEXA	Dual-energy X-ray Absorptiometry
EMR	Electronic medical record
FDA	Food and Drug Administration
IRB	Institutional Review Board
MVC	Maximal voluntary contraction (of the quad muscles)
NIH	National Institutes of Health
PBFR	Personalized Blood Flow Restriction
PT	Physical Therapist
RIOA	Reynolds Institute on Aging
ROM	Range of Motion (of the knee joint)
UAMS	University of Arkansas for Medical Sciences
UPIRTSO	Unexpected problem involving risks to subjects or others

Study Schema

Surgeon collaborators or their designees screen their orthopedic clinic for eligible subjects and send referrals to study staff via UAMS email.

Study staff contact referrals via phone or email to discuss consent process.

Visit 1: Subjects come to RIOA for informed consent process prior to surgery.
Randomization (1:1) occurs.

Visit 2: Approx. 7-10 days prior to surgery, subjects come to RIOA for baseline testing.

Subjects undergo scheduled knee surgery at UAMS

***Prescribed physical therapy begins with or without BFR per randomization at UAMS
Colonel Glenn facility***

Visit 3: Subjects come to RIOA for post-operative testing approx. 8 weeks postop.

Prescribed physical therapy continues with/without BFR per randomization

Visit 4: Approx. 12 weeks postop, subjects come to RIOA for mid-point testing.

Visit 5: Approx. 16 weeks postop, subjects come to RIOA for end-point testing.

Use of Blood Flow Restriction + Standard of Care Physical Therapy to Improve Functional Outcomes after
Anterior Cruciate Ligament Reconstruction
PI: [name].
Institution: UAMS
Sponsor: UAMS

Study Calendar

Procedure	Visit 1	Visit 2	Visit 3	Visit 4	Visit 5
Informed consent	X				
10-meter walk test		X	X	X	X
bilateral MVC		X	X	X	X
DEXA scan		X	X	X	X
In Body scan		X	X	X	X
Stair ascent			X	X	X
Stair descent				X	X
Y-balance test			X	X	X

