1.0 Protocol Summary

This will be a randomized pilot study to determine the effectiveness of Personalized Blood Flow Restriction (PBFR) technique in conjunction with prescribed physical therapy (PT) in a cohort of anterior cruciate ligament (ACL) reconstruction subjects. Both groups of subjects will undergo unilateral ACL reconstruction at University of Arkansas for Medical Sciences (UAMS), followed by prescribed PT at the UAMS Orthopedic Clinic at Colonel Glenn.

Up to 25 subjects will be enrolled. Half are randomized to the BFR group with the other will perform PT without BFR.

Data collection will occur at four approximate occasions: pre-surgery, 8-weeks postop, 12-weeks postop, and 16-weeks postop.

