4.0 Study Population

Up to 25 subjects of any gender or ethnicity will be enrolled with a target of n=20 for study completion.

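### The four test points are justified by the course of recovery, but section 10.1 tests weeks 12 and 16 only, leaves week 8 out of every comparison and estimates no arm-by-visit contrast

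*Combined protocol and SAP*

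**What the plan says.** Section 1.0 sets the schedule: "Data collection will occur at four approximate occasions: pre-surgery, 8-weeks postop, 12-weeks postop, and 16-weeks postop". Section 2.1 gives the reason for it: "This testing schedule will identify progress in functional outcome recovery over the course of rehabilitation". The same section states the purpose: "The goal of this pilot project is to demonstrate the potential to steepen the healing curve after ACL repair".

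Section 10.1 then says that, for each strength and functional outcome, "the difference between the two groups by the mid-point and final visit will be tested", two-sided at 0.05. The ANCOVA has a group term with the pretest as covariate. The Study Schema identifies the two visits: "Visit 4: Approx. 12 weeks postop, subjects come to RIOA for mid-point testing" and "Visit 5: Approx. 16 weeks postop, subjects come to RIOA for end-point testing". A generalized linear mixed model is named only as an alternative when ANCOVA assumptions fail, and its terms are not listed.

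Section 4.0 allows up to 25 subjects "with a target of n=20 for study completion". The documents give no rule for missing visits. Section 8.0 says the cuff is used mainly in the early part of rehabilitation.

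**The concern.** The design collects a recovery curve and the analysis plan compares two points on it. A group-plus-pretest ANCOVA at one visit has no visit term, so it cannot say whether the arms moved closer or further apart between visits. The week-8 test is the one nearest to the period in which section 8.0 says BFR is mostly used, and it is the one left out. If the benefit is early and the control arm later catches up, the planned tests are badly placed to see it.

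A second, smaller matter is that the week-16 ANCOVA can use only subjects with a week-16 value. Their week-8 and week-12 results carry information about week 16 that this model does not use. At stake are a modest loss of precision and, if leaving is selective, some avoidable bias.

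**Working it through.** The plan gives no power calculation, SD or between-visit correlation, so there is no figure to reproduce. All results below are in SD units under assumed correlations.

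**1. Purpose against model.** Section 2.1 wants progress over the course of rehabilitation. The model terms in 10.1 are group and pretest: no visit, no group-by-visit, no subject effect. That the two visits are analysed in separate ANCOVAs is an inference, but it is the natural reading of such a model applied at two visits.

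**2. What the planned tests can distinguish.** Simulation: 10 completers per arm (20 at 1:1), SD 1, correlation 0.7 between all test points, 4,000 runs, two-sided 0.05. The contrast is the arm difference in change from week 8 to week 16, adjusted for pretest.

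| Arm gap at weeks 8, 12, 16 (SD) | Week-12 ANCOVA | Week-16 ANCOVA | Contrast, weeks 8 to 16 |
|---|---|---|---|
| 1, 1, 1 | 82% | 82% | 5% |
| 0, 0.5, 1 | 32% | 81% | 75% |
| 1, 0.5, 0 | 30% | 4% | 76% |
| 0, 0, 0 | 5% | 5% | 5% |

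The week-16 test cannot tell rows 1 and 2 apart. In row 3 both planned tests do poorly. A week-8 ANCOVA would reject about 82% of the time in row 3: the gap there is 1 SD and the residual variance, 1 - 0.7² = 0.51, is the same at every visit in this setting.

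**3. Precision at week 16.** Take 5 of 25 missing Visit 5 at random, all with week-8 and week-12 values (12.5 per arm on average, 10 of them complete). The ratio of ANCOVA to mixed-model variance is 1 / (1 - 0.2 R²). Here 0.2 = 1 - 20/25, and R² is the share of week-16 variance, given pretest, explained by weeks 8 and 12.

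For equal correlations of 0.7:
- residual covariance 0.7 - 0.49 = 0.21; residual correlation 0.21 / 0.51 = 0.412
- R² = 2 × 0.412² / 1.412 = 0.240
- ratio = 1 / (1 - 0.048) = 1.05
- SE = √(2 × 0.51 / 10) = 0.319 for ANCOVA, against 0.312

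Over correlations 0.5 to 0.9 the ratio is 1.03 to 1.07 with equal correlations and 1.05 to 1.14 with AR(1), or 10.3 to 11.4 effective subjects per arm instead of 10. A simulation with arms of 12 and 13, two of the five also missing week 12, pretest correlation 0.5-0.7 and posttest correlation 0.7-0.9 gives 1.05 to 1.16. Together this is roughly 3-16%. A repeat of that simulation that added AR(1) posttest correlations (3,000 runs per setting) spread more widely, about 0-21%.

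**4. Precision of the between-visit contrast.** Same setting, correlation 0.7, variances per arm:
- week 8: 0.51 / 12.5 = 0.0408
- week 16: (0.51 / 10) × 0.952 = 0.0486
- covariance: 0.21 / 12.5 = 0.0168
- difference: 0.0408 + 0.0486 - 2 × 0.0168 = 0.0558

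Two arms give SE = √0.1116 = 0.334. The gap detectable with 80% power is (1.960 + 0.842) × 0.334 = 0.94 SD. Over the assumed correlations it runs from 0.54 to 1.39 SD.

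**5. Selective leaving (mechanisms assumed).**
- Three or four BFR leavers tend to be slow at week 8 and one or two controls leave at random: the completer ANCOVA overstates BFR by about 0.05-0.25 SD; the likelihood estimate is within about 0.02 SD of the truth.
- BFR leaving depends on the unseen week-16 result: the likelihood estimate is itself off by 0.05-0.15 SD, the ANCOVA by 0.19-0.26 SD.
- Slow recoverers leave both arms (2 BFR, 3 control): ANCOVA bias is about 0.04-0.05 SD.

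The standard error of the week-16 ANCOVA in these runs is about 0.33-0.40 SD, larger than any of these biases.

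**The case against.** The strongest defence is that the only Specific Aim (section 3.0) concerns the effect on muscle mass, strength and function, not a rate, and that the healing curve appears only in the Significance text. A pretest-adjusted difference at week 12 or 16 does estimate how much further one arm has recovered since before surgery. A reader might therefore infer that the plan gives no estimate of recovery at all; that is not so. What is missing is week 8 and a formal contrast between post-operative visits.

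A reader might also infer that 10.1 throws away the earlier results of anyone who misses the final visit. The text does not support that: their week-12 value still enters the mid-point ANCOVA. It is week 8 that goes untested, and for completers too.

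A third point stands and shapes the fix. A contrast starting at week 8 would miss steepening that had already happened by week 8: the constant gap in the table is found 82% of the time by the planned ANCOVAs and 5% by the contrast. The week-8 difference must therefore be reported beside the contrast, not replaced by it.

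Finally, the gain in precision requires that leavers have post-operative data. Randomisation is at Visit 1, before baseline testing and surgery, and anyone lost before Visit 3 adds nothing to either model.

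**Conclusion.** The concern holds in a limited form. Section 10.1 does not match the use that section 2.1 makes of the repeated tests: week 8 enters no comparison, no group-by-visit contrast is estimated, and a subject without Visit 5 contributes nothing to the week-16 estimate. The mixed-model fallback does not cure this, because it applies only when assumptions fail and has no stated terms.

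The unanswered question is the main loss. The variance penalty at week 16 is modest, roughly 3-16%, if 5 of 25 miss that visit at random with earlier data in hand and the correlations are as assumed. It would be tempting to conclude that the final-visit estimate is biased. The documents give no dropout rate, direction or mechanism, and 25 for 20 may simply be a recruitment margin. Bias of about 0.05-0.25 SD follows only if leaving depends on observed earlier results and differs by arm; a mixed model reduces it in that case, but does not remove bias when leaving depends on unseen week-16 results.

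**What to change.** In section 10.1, make one baseline-adjusted repeated-measures mixed model per outcome the main analysis:

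- Terms: group, visit as a category (weeks 8, 12, 16), group-by-visit, and pretest-by-visit where a pretest exists. Use an unstructured or simpler covariance and Kenward-Roger degrees of freedom.
- Include every randomised subject with at least one post-operative value, and add a statement on missing visits and the assumption made about them.
- The Study Calendar starts stair ascent and Y-balance at Visit 3 and stair descent at Visit 4. These three outcomes have no pretest term, and stair descent uses weeks 12 and 16 only.
- Report the adjusted arm difference at each visit, including week 8 (which captures early steepening), and the arm difference in change between post-operative visits, each with a 95% confidence interval. Present them as estimates: the between-visit contrast has 80% power only at about 0.5-1.4 SD. That suits the stated aim of obtaining data to power later studies.

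The cost is SAP wording and a standard SAS procedure, with no new data. The downside is that a few covariance parameters must be estimated from about 25 subjects.
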